5.2. The size of the sample under study

The estimation of the sample size of subjects was based on the following parameters:

- bilateral significance level $\alpha=0.05$ Z value = 1.96;
- statistical power level is 80%, Z-value = 0.84;
- method of sample formation — randomization using elements of randomness;
- statistical criteria used are two-sided due to the lack of a posteriori information about the superiority of the effect of the study drug over the placebo effect.

Calculation results:

- number of volunteers who must complete participation in the study in accordance with the protocol is 286 in the group or a total of 572 participants.
- number of randomized participants is 315 in a group or total 630 people
- number of screened volunteers – up to 642.

5.3. Missing / incorrect data

For all parameters, the analysis will be carried out only on the available information, without filling in the data. There are no plans to use data reconstruction methods in this study.

5.4. Deviations from the protocol and the original statistical plan

An additional analysis is planned for the sensitivity of the results of the evaluation of the primary endpoint, depending on the vaccination status.

To maintain the balance and comparability of the groups, as well as to exclude the influence of the period of active antibody formation caused by the vaccine ⁸on the results, as part of an additional analysis, a subpopulation of participants vaccinated with at least one dose of the drug during participation in the study will be excluded from both groups.

⁸Due to the small proportion of vaccinated participants, the number of doses of the vaccine received by the participant and its type (trade name) will not be taken into account

Participants vaccinated prior to inclusion in the study will be included in a modified sample with the formation of a separate population "not vaccinated during the study" to achieve the necessary statistical power.

The conditions for the uniform distribution of patients by vaccination status between groups will be checked beforehand.

All changes in the initial statistical plan with their justification will be reflected in the final report on the clinical trial.

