3. EVALUATION OF EFFECTIVENESS PARAMETERS

3.1. Endpoints of the study

The primary criterion of effectiveness is the proportion of patients with acute respiratory viral infections, including COVID-19, at the end of the period of preventive administration of the drug (measurement time: 28 days).

The scientific hypothesis is that the prophylactic administration of Ingaron will lead to a decrease in the incidence of acute respiratory viral infections, including COVID-19, among adult volunteers.

The preventive efficacy of the study drug will be evaluated by the following primary and secondary endpoints.

Primary endpoint:

The proportion of patients with acute respiratory viral infections, including COVID-19, at the end of the period of preventive administration of the drug (measurement time: 28 days).

Secondary endpoints:

1. The proportion of patients with confirmed COVID-19 at the end of the period of preventive treatment of the drug (measurement period: 28 days).
2. The proportion of patients with acute respiratory viral infections, including COVID-19, at the end of the follow-up period (change period: 2 months).
3. The proportion of patients with confirmed COVID-19 at the end of the follow-up period (change period: 2 months).
4. Frequency of development of complicated course of ARVI.
5. The proportion of participants with each of the scores (0-8) according to the WHO Clinical Improvement Scale (change period: 28 days).
6. The proportion of participants with each of the scores (0-8) according to the WHO Clinical Improvement Scale (change period: 2 months).
7. Duration of symptoms of the disease of study participants who had acute respiratory viral infections, including COVID-19 (change period: 2 months).
8. The duration of the symptoms of the disease of the study participants who were infected with ARVI, including COVID-19 (measurement period: 28 days).

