5.5. Populations of participants for analysis

The following populations will be formed for analysis: ITT, PP and safety; additionally: ITT_NV, PP_NV, ITT_NV_BE, PP_NV_BE.

Statistical data analysis will be carried out in the following populations of participants:

1. Population of all included and randomized participants (intention-to-treat, ITT): all randomized participants who were exposed to the study drug, regardless of the degree of protocol compliance during the study. This data set is the main one for the analysis of primary and secondary effectiveness parameters;
2. Population of participants who completed the study according to the protocol (per protocol, PP): all randomized subjects who completed participation in the study in accordance with the protocol (completed the prescribed period of treatment and follow-up without significant deviations from the protocol). This data set is additional for the analysis of primary and secondary effectiveness parameters;
3. Safety population: The data set analyzed for safety assessment is identical to the ITT data set. However, unlike the population depending on the prescribed treatment, participants are analyzed depending on the actual treatment (if it differs from the treatment that was prescribed by randomization). All types of safety analysis will be based on the use of a data set for security assessment;
4. Modified population of all included and randomized participants (intention-to-treat, ITT) not vaccinated against COVID-19: ITT_NV. This data set is additional for the analysis of the primary efficiency parameter;
5. Modified population of participants who completed the study according to the protocol (per protocol, PP), not vaccinated against COVID-19: PP_NV. This data set is additional for the analysis of the primary efficiency parameter;
6. Modified population of all included and randomized participants (intention-to-treat, ITT) not vaccinated against COVID-19 or vaccinated before inclusion in the study: ITT_NV_BE. This data set is additional for the analysis of the primary efficiency parameter;
7. Modified population of participants who completed the study according to the protocol (per protocol, PP), not vaccinated against COVID-19 or vaccinated before inclusion in the study: PP_NV_BE. This data set is additional for the analysis of the primary efficiency parameter.

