Thus, the safety population will be used to present demographic data about participants, as well as for safety assessment. ITT will be considered the main sample for comparative analysis of performance parameters. The PP population will include only participants who completed the study without critical deviations from the protocol and will be formed as an additional sample to evaluate the effectiveness parameters in order to analyze the sensitivity of the results obtained in the ITT population. The modified populations will be used to perform sensitivity analysis when evaluating the primary endpoint.

The number of participants who must complete the study in accordance with the protocol is 286 in each group, or a total of 572 participants.

The number of randomized participants is 315 in each group or total of 630 participants.

The number of screened participants is up to 642.

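### The four vaccination sensitivity sets exclude anyone vaccinated at any time during participation, including after the Day 28 outcome, so they lose the protection of randomisation and could bias the comparison

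*SAP*

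**What the plan says.** SAP 5.4 adds a sensitivity analysis of the primary endpoint by vaccination status, in which "a subpopulation of participants vaccinated with at least one dose of the drug during participation in the study will be excluded from both groups". It gives two reasons: "To maintain the balance and comparability of the groups, as well as to exclude the influence of the period of active antibody formation". Footnote 8 describes the vaccinated share of participants as small, without a figure. As a safeguard, "The conditions for the uniform distribution of patients by vaccination status between groups will be checked beforehand", and Table 24 is laid out to compare vaccination status by group in all six populations.

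SAP 5.5 defines two pairs of sets. ITT_NV and PP_NV hold people "not vaccinated against COVID-19: ITT_NV" (PP_NV likewise). ITT_NV_BE and PP_NV_BE hold people "not vaccinated against COVID-19 or vaccinated before inclusion in the study: ITT_NV_BE" (PP_NV_BE likewise). None of the four definitions has a time limit. On their role, "The modified populations will be used to perform sensitivity analysis when evaluating the primary endpoint". That endpoint is read "at the end of the period of preventive administration of the drug (measurement time: 28 days" (SAP 3.1).

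The Protocol's design section puts total participation at 56–62 days. For a participant with an ARVI case the final visit may come earlier or later, up to 90 days in all. The study is open-label (SAP 2.3).

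**The concern.** Whether someone is vaccinated during the study is decided after randomisation, in an open-label trial, and may depend on both arm and health. A set defined by that decision is no longer the randomised comparison. Here the decision can also come after the outcome. A participant who reached Day 28 without ARVI and was vaccinated on Day 45 would be removed, although the Day 28 result was already fixed. The same holds for someone vaccinated after ARVI onset.

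If illness delays vaccination, cases tend to stay in the set while some non-cases leave it, so the observed rate rises. If that happens to different degrees in the two arms, the risk ratio moves with no drug effect behind it. A sensitivity analysis that shifts for this reason could be misread as support for the main result, or as a contradiction of it.

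**Working it through.** **1. Exclusion window against the outcome.** The endpoint is read at 28 days (SAP 3.1). Participation is 56, 62 or at most 90 days (Protocol, design section). The share of the window after the outcome is (T − 28)/T:
- T = 56: 28/56 = 50%
- T = 62: 34/62 = 55%
- T = 90: 62/90 = 69%

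Doses in that part cannot alter a Day 28 result, so the antibody-formation reason does not cover them. This step needs no assumption about uptake. Because the final visit moves for ARVI cases, the window can also differ in length between cases and non-cases.

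**2. Effect on the comparison.** The documents give no in-study uptake by arm or by case status, so the values below are assumptions. Let p be the true Day 28 incidence, v the in-study uptake among non-cases, and r the uptake of cases as a fraction of v. Then

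rate after exclusion = p(1 − rv) / [p(1 − rv) + (1 − p)(1 − v)]

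Take p = 5% in both arms (no drug effect; 5% is the top of the Protocol's assumed control range of 1–5%). With r = 0, meaning no case is vaccinated afterwards:
- v = 0%: 0.0500
- v = 5%: 0.05/(0.05 + 0.9025) = 0.0525
- v = 10%: 0.05/(0.05 + 0.855) = 0.0552
- v = 20%: 0.05/(0.05 + 0.76) = 0.0617

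| Uptake, Group I vs Group II | RR, r = 0 | RR, r = 0.5 | RR, r = 1 |
|---|---|---|---|
| 0% vs 10% | 0.905 | 0.95 | 1.00 |
| 5% vs 20% | 0.85 | 0.92 | 1.00 |
| 0% vs 20% | 0.81 | 0.89 | 1.00 |
| 10% vs 10% | 1.00 | 1.00 | 1.00 |

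If the higher uptake is in Group I, the ratios invert; 20% vs 0% with r = 0 gives 1/0.81 = 1.23. If uptake is as low as footnote 8 suggests, the shift is small: with r = 0, an assumed 2% vs 5% gives 0.97 and 0% vs 5% gives 0.95.

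**3. Could it look like a finding?** In the most extreme row (0% vs 20%, r = 0), 315 per arm gives about 315 × 0.05 ≈ 16 cases in each arm. Group I keeps 315 people, and Group II keeps 315 × (0.05 + 0.95 × 0.80) ≈ 255. Comparing 16/315 with 16/255 gives RR 0.81, 95% CI 0.41–1.59, Fisher p = 0.59.

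**4. The safeguard.** Table 24 splits participants only into vaccinated and not vaccinated. It does not show whether a dose came before or after Day 28 or ARVI onset, and the SAP states no action if the arms differ. In the two NV sets everyone is unvaccinated by definition, so the comparison there is empty.

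**The case against.** The strongest reply is that this is a supportive analysis and its bias is conditional. SAP 5.5 calls every modified set additional and keeps ITT as the main set, which this rule does not touch. A false effect needs uptake that differs by arm and is also linked to illness; without either one the risk ratio stays at 1.00. The documents establish neither. Footnote 8 says few participants are vaccinated, and a balance check is planned. Even the extreme case in the working comes nowhere near significance. All of that stands, and it limits the weight of the point.

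A reader might infer that unequal uptake is built in, because the Protocol bars preventive medications in Group I and allows them in Group II (interferon gamma excepted). The documents do not say whether a vaccine counts as such a medication, and vaccination status is recorded separately in the anamnesis. The asymmetry makes unequal uptake plausible and no more.

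The reply does not rescue the missing date limit. No uptake pattern makes a dose after Day 28 relevant to a Day 28 outcome, and an even split of vaccination status would not show that the people remaining in each arm are comparable. Removing participants vaccinated before inclusion, as the NV sets do, is a baseline selection and is not at issue.

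**Conclusion.** The point holds as a defect in how the four sets are defined. They depend on a post-randomisation event that can follow the outcome, so the SAP's stated aim, "To maintain the balance and comparability of the groups", cannot be relied on. The antibody-formation reason fails for doses after Day 28 or after ARVI onset.

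Any bias in the risk ratio is possible but unproven, and its direction is unknown. Under no drug effect it ranges from none (equal uptake, or uptake unrelated to illness) to 0.81 at an assumed 0% versus 20% with no case vaccinated afterwards. It is likely modest given footnote 8. The documents do not support the stronger readings that the sets will manufacture a benefit, or that the primary result itself is compromised. The change is worth making because it is specific and cheap.

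**What to change.** 1. In SAP 5.4 and 5.5, state that no participant is excluded for a dose given after ARVI onset or after Day 28.
2. Define vaccination subgroups by status at randomisation, which the Protocol already collects in the anamnesis (schedule of procedures, note 2). Analyse the full ITT set stratified by it, with a Mantel-Haenszel risk difference.
3. Keep the aim of removing in-study antibody formation through a supportive analysis of time to first ARVI up to Day 28, censored at the first in-study dose. State that it assumes non-informative censoring, since it too depends on behaviour after randomisation.
4. Extend Table 24 to show in-study uptake by arm and by timing (before or after ARVI onset or Day 28), and say what follows if the arms differ.

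The cost is SAP wording and a little programming. Items 3 and 4 need dose and onset dates; the documents do not clearly say that dates of in-study doses are collected, so this should be confirmed first. The heading of SAP 5.4 already marks the analysis as a departure from the original plan, so little further labelling is needed.

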In this study, the main parameter of effectiveness is the proportion of patients with acute respiratory viral infections, including COVID-19, at the end of the period of preventive administration of the drug. The study is planned to show that in the study group, the number of patients with acute respiratory viral infections, including COVID-19, will be significantly less compared to the control group.

The efficiency parameter was selected based on international recommendations for manufacturers of medicines and biological products [28].

The null hypothesis will be tested by comparing the number of cases in the two groups at the end of the period of preventive administration of the drug. It is expected that at least 90% of randomized patients will be suitable for inclusion in the population of the primary analysis (PP). The statistical purpose of the study is a comparative study of the effectiveness of the preventive regimen of the drug. In the main group of study I, study drug Ingaron 100,000 IU, lyophilizate, will be used to prepare a solution for intranasal administration, 1 time a day every other day for 10 days with a repeat of the 10-day course of preventive administration after 7 days of interruption.

To estimate the sample size in this study, an 80% power level was taken (P – probability of not missing the present effect is 0.8) and a one-sided level of statistical significance of 5% (α – the probability of making an erroneous decision about the presence of an effect is less than 0.05). The statistical criteria used are one-sided due to the availability of information about the superiority of the effect of the study drug over the lack of preventive measures against the nosology being studied [28].

Thus, the sample size was calculated based on the following parameters:

- at the required significance level $\alpha = 0.05$, the value of $Z = 1.96$;
- level of statistical power is assumed to be 80%, the value of $Z = 0.84$;
- method of sample formation – randomization using random elements.

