The primary criterion of effectiveness is the proportion of patients with acute respiratory viral infections, including COVID-19, at the end of the period of preventive administration of the drug (measurement time: 28 days). Secondary efficacy criteria: proportion of patients with confirmed COVID-19 at the end of the period of preventive administration of the drug (measurement period: 28 days); proportion of patients with acute respiratory viral infections, including COVID-19, at the end of the follow-up period (change period: 2 months); proportion of patients with confirmed COVID-19 at the end of the follow-up period (period of change: 2 months); and the frequency of development of complicated course of ARVI.

The literature analysis conducted on similar studies of the effectiveness and safety of the use of interferon-gamma shows that the incidence of ARVI can be observed in 2% of cases in the main group of patients taking interferon gamma, as well as in 14% of the control group taking alternative methods of protection and representing medical workers working in the "red zone" and those at high risk through frequent and prolonged contact with infected patients ($p < 0.05$).

Provided incidence in the control group is from 1 to 5% (taking into account the assumption that the incidence in the control group will be approximately equal to the average incidence of the general population) [29], and incidence in the study group will be at least 3% lower (which can already be considered a minimally clinically significant decrease in incidence in the absence of preventive measures with proven effectiveness, which could be taken as a standard), minimum sample size should be 630 patients (taking into account 10% of early retirement). Such a sample size will also make it possible to establish a decrease in incidence by 4% or more when incidence is set at up to 8% in the control group and a decrease in incidence by 6% or more when the incidence is set at up to 18% in the control group (Table 1 – Dependence of the sample size on various parameters).

The calculation of the required sample size was performed using a formula for calculating the sample size for a qualitative sign [30]:

$$n = \frac{P_1 * Q_1 * t^2 + P_2 * Q_2 * t^2}{(P_1 - P_2)^2}$$

Note to the formula:

P – proportion of cases in which the study sign occurs,

Q – proportion of cases in which the study sign does not occur,

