6. TABLE PATTERNS

Table1. Distribution of subjects

Distribution of subjects	Group I (proportion, %)	Group II (proportion, %)
Included in the study (screened)	n/N (%)	
Of these:		
Excluded at the screening stage:	n/N (%)	
Randomized	n/N (%)	n/N (%)
Prematurely excluded, out of them:	n/N (%)	n/N (%)
Existence of exclusion criterion #X (description)	n/N (%)	n/N (%)
Population safety	n/N (%)	n/N (%)
ITT population	n/N (%)	n/N (%)
Population PP	n/N (%)	n/N (%)

Table2. Demographic and anthropometric characteristics of subjects at the time of inclusion (safety population)

Group	Parameter	Age (years)	Weight (kg)	Height (cm)	Smoking index (p/y)	Frequency of acute respiratory infections (amount/g)
GROUP I	n					
	M					
	CO					
	min.					
	max.					
	Me					
GROUP II	n					
	M					
	CO					
	min.					
	max.					
	Me					
p (between groups)						

Table3. Distribution of subjects by gender (safety population)

Gender	GROUP I	GROUP II
Male	n/N (%)	n/N (%)
Female	n/N (%)	n/N (%)
p (between groups)		

Table4. Distribution of subjects by race (safety population)

Race	GROUP I	GROUP II
Caucasian	n/N (%)	n/N (%)
Mongoloid	n/N (%)	n/N (%)
Negroid	n/N (%)	n/N (%)
p (between groups)		

Table5. Medical history (safety population)

Parameter	Value	Group I (N =)	Group II (N =)
Diagnosis (chronic disease)	...	n/N (%)	n/N (%)
Diagnosis (according to anamnesis)	...	n/N (%)	n/N (%)
p (between groups)			

Table 6. Methods of nonspecific prevention (safety population)

Type	Frequency	GROUP I	GROUP II
Total subjects		N =	N =
Masks	Yes	n/N (%)	n/N (%)
	No	n/N (%)	n/N (%)
	Sometimes	n/N (%)	n/N (%)
Respirator	Yes	n/N (%)	n/N (%)
	No	n/N (%)	n/N (%)
	Sometimes	n/N (%)	n/N (%)
Gloves	Yes	n/N (%)	n/N (%)
	No	n/N (%)	n/N (%)
	Sometimes	n/N (%)	n/N (%)
Glasses	Yes	n/N (%)	n/N (%)
	No	n/N (%)	n/N (%)
	Sometimes	n/N (%)	n/N (%)
Surgical overalls	Yes	n/N (%)	n/N (%)
	No	n/N (%)	n/N (%)
	Sometimes	n/N (%)	n/N (%)
p (between groups)			

Table 7. Drug allergy (safety population)

	GROUP I	GROUP II
Total subjects	N =	N =
No	n/N (%)	n/N (%)
Yes	n/N (%)	n/N (%)
p (between groups)		

Table 8. Results of the assessment of the incidence rate at the end of the prevention period (ITT/PP/ITT_NV/PP_NV/ITT_NV_BE/PP_NV_BE population)

	GROUP I	GROUP II
Total subjects	N =	N =
ARVI	n/N (%)	n/N (%)
Not sick	n/N (%)	n/N (%)
p (between groups)		

Table 9. Results of the assessment of the incidence of COVID-19 at the end of the prevention period (ITT population, PP)

	GROUP I	GROUP II
Total subjects	N =	N =

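### SAP 5.4 credits the sets that retain pre-study vaccinees with necessary power, but no calculation supports this and no interval is planned when a set loses significance

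*SAP*

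**What the plan says.** SAP 5.4 plans an additional sensitivity analysis of the primary endpoint by vaccination status. Participants vaccinated during the study are excluded from both groups. Those vaccinated before inclusion are retained, and the reason given is "to achieve the necessary statistical power".

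SAP 5.5 defines four modified sets. ITT_NV and PP_NV contain only the unvaccinated. ITT_NV_BE and PP_NV_BE add back the pre-study vaccinees; item 7, for example, reads "not vaccinated against COVID-19 or vaccinated before inclusion in the study: PP_NV_BE". All four are labelled additional, and ITT remains the main set.

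The only size that the SAP links to power is in 5.2, repeated in 5.5: "The number of participants who must complete the study in accordance with the protocol is 286 in each group", with 315 per group randomised. Section 5.2 adds "statistical criteria used are two-sided" and "statistical power level is 80%, Z-value = 0.84". Footnote 8 to 5.4 describes the vaccinated share as small and gives no figure.

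Table 8 in SAP 6 ("Results of the assessment of the incidence rate at the end of the prevention period") covers ITT, PP and the four modified sets with n/N (%) and a p-value. SAP 5.1 plans confidence intervals for the size of a group difference only where that difference is statistically significant. It plans 95% intervals around proportions for secondary endpoints, but not for the primary one.

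**The concern.** The power phrase tells the reader that the NV_BE sets are large enough for their purpose. If ITT is significant and ITT_NV_BE is not, a reader who accepts that will conclude that the drug effect depended on vaccination. The same pattern can arise simply because there are fewer participants.

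The reporting plan does not help to tell the two apart. The interval for the difference, which would show whether the estimate moved or only became less precise, is planned only for significant comparisons. It is absent in exactly the case where it is needed. The SAP also has no rule for deciding whether a modified set agrees with ITT.

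**Working it through.** **Inputs.** Two-sided alpha 0.05 with Z = 1.96, power 80% with Z = 0.84, 286 and 315 per group (SAP 5.2). The SAP states no event rates. The protocol (Number of participants) says that "incidence in the control group is from 1 to 5" per cent, with a reduction of at least 3 points; the 315 cell of protocol Table 1 is the 5% row, so the planning rates are 5% v 2%. Planned loss is 10%. The share vaccinated during the study is not given, so removal rates are assumed and taken as equal in both groups.

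**1. The plan's own figure.** The protocol formula is n = (P1Q1 + P2Q2)t² / (P1 − P2)².
- P1Q1 + P2Q2 = 0.05 × 0.95 + 0.02 × 0.98 = 0.0671
- n = 0.0671 × 1.96² / 0.03² = 286.4
- 286.4 × 1.1 = 315.1

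Both figures reproduce. The formula contains only t, so the 0.84 for power is never used. With it, n = 0.0671 × (1.96 + 0.84)² / 0.03² = 585 per group; the pooled-variance version gives 588.

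**2. Power at 5% v 2%.** Exact binomial enumeration, two-sided, using the SAP 5.1 rule: Fisher if the smallest expected count is below 5, Yates if 5 to 10, otherwise Pearson.

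| Per group | SAP rule | Pearson throughout |
|---|---|---|
| 315 (all randomised) | 51.7% | 54.7% |
| 286 (stated completers) | 45.8% | 50.7% |
| 255 (10% loss, then 10% removed) | 39.1% | 46.3% |

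No modified set can be larger than ITT, so none reaches 80% at these rates. The protocol instead specifies "a one-sided level of statistical significance of 5" per cent. One-sided power by the normal approximation is 65.7% at 315 and 62.1% at 286, which is still short.

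**3. Headcount against 286.**
- ITT_NV_BE: 315 − 286 = 29 removals per group are possible before it falls below 286, and 29/315 = 9.2%.
- PP_NV_BE: with the planned 10% loss, 315 × 0.9 = 283.5, already below 286 before any vaccinee is removed. If PP meets 286 exactly, the first removal takes it below.

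**4. Loss of significance from removal alone.** Simulation with 315 per group at 5% v 2%, removing participants at random so that vaccination has no influence. Share of ITT-significant trials that are not significant after removal:

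| Removed | SAP rule | Pearson throughout |
|---|---|---|
| 3% | about 6% | about 5% |
| 5% | about 10% | about 8% |
| 10% | about 17 to 18% | about 13 to 14% |

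The columns differ because removal can trigger the Yates correction: the average expected number of cases per group is 315 × 0.035 = 11.0 before removal and 284 × 0.035 = 9.9 after 10% is removed.

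**The case against.** The strongest reply is that the phrase is read too literally. In context it explains why pre-study vaccinees are kept, and keeping them does make the NV_BE sets larger than the NV sets. The text is translated, the sets are supplementary, and no primary conclusion rests on them. This stands as a limit on seriousness. It does not supply the missing calculation, because the sentence still attributes adequate power to the resulting sets.

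A reader might go further and infer that, by the SAP's own numbers, these sets cannot have the required size. The documents do not support that. ITT_NV_BE keeps 286 per group with up to 9.2% removed, and the only statement on vaccination is that the share is small. PP_NV_BE is short for certain only if the full 10% loss occurs, which the protocol treats as possible rather than expected.

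Nor is removal the main cause of low power. By the normal approximation, two-sided power is 53.5% at 315 and 49.7% at 286, so removing about 9% costs roughly 4 points. Most of the gap to 80% exists before anyone is excluded.

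The power result also depends on the rates. By the same approximation, 286 per group gives 80.2% for 5% v 1%, 80.5% for 10% v 4%, and close to 100% for the 14% v 2% that the protocol cites from the literature. The SAP does not argue from any of these.

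Finally, the SAP does not say that sensitivity is judged by p, and Table 8 prints percentages from which a risk difference can be read. That is correct, but a difference without an interval does not show whether two sets are compatible.

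**Conclusion.** The point holds, with limited reach. SAP 5.4 makes an unsupported statement about power. At the planning rates the true figure is about 52% for the full randomised set and about 46% at 286 per group under the SAP's test rule, and lower in any smaller set. This is mainly inherited from the base sample size.

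The practical gap is in reporting. With 3 to 10% removed, about 5 to 18% of ITT-significant results would lose significance with no change in effect, and no interval is planned for those cases. These figures assume 5% v 2%, random and equal removal in both groups, and removal rates that the documents do not give. Rates of 20 to 30% would produce larger losses but fit poorly with a share described as small, so the case does not rest on them. The main ITT analysis is unaffected.

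**What to change.** - In SAP 5.4, delete the power phrase. State that the four modified sets have no stated power and have less than the ITT or PP set from which each is drawn.
- In Table 8, report the risk difference (or ratio) with its 95% CI for ITT, PP and all four modified sets, whether or not the test is significant. Amend the conditional sentence in SAP 5.1 to match.
- State that sensitivity is judged by comparing the estimates and intervals with those from ITT, not by whether p stays below 0.05.

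The cost is some SAP wording and one extra row in a table shell, with no additional participants or data. The sponsor gives up a favourable claim. The change does not repair the base sample size, which needs its own correction.
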